2.0	5.2, 8.4, 11.0	Procedure time changed from bronchoscope in/out to locatable guide in/out.	This change adequately captures the actual procedure of ENB, and leaves out other procedures that could occur at the same visit.
2.0	8.3	Changed the requirement of an investigator to be medically licensed rather than board certified.	Board certification language was part of the template CIP. For purposes of this study, having a Medical License is sufficient.
2.0	8.6.4.1, 8.6.5	Moved smoking history into the medical history assessment. Clarified what medical histories would be collected.	Since smoking history is part of a medical history, and other aspects of a medical history are to be collected, clarification on medical history was made.
2.0	8.6.4.3	Removed the requirement of the 1-month visit to be conducted in person, and added the allowance of 1-month visits to be conducted via phone.	A 1-month post procedure visit is not typically standard of care for most sites. This is affecting enrollment and subject returns for 1-month visit. All 1-month visit data can be easily collected via phone.
2.0	9.3	Lowered the maximum enrollment per site from 250 to 75.	This was to help the study to collect data at a wide range of different sites. Certain regions may decide to have a lower cap for their region.
2.0	n/a	Minor updates (such as contact information) and minor clarifications were made throughout the protocol. These minor changes did not affect the purpose or requirements of the study.	Minor updates and clarifications were needed in the protocol to meet global regulatory requirements or to provide contact updates or to make minor corrections.
2.1	4.0, 8.2.2, 8.6.4.3, 8.6.5	Changed the name of the added questionnaire “Electromagnetic Navigation Bronchoscopy Productivity and Activity Questionnaire (ENB-PAQ)”	Name change required.

18.1 Sample Patient Informed Consent37

18.2 Lung Cancer Staging37

4.0 Protocol Synopsis

Background and Rationale of the Study	
Study Objective	The objective of this prospective, single-arm, multicenter, post-market, observational, study is to evaluate outcomes following electromagnetic navigation bronchoscopy (ENB) procedures using the superDimension™ navigation system.
Test Device	superDimension™ Navigation System
Control or Comparator	Not applicable
Study Design	
Study Type	Prospective, single-arm, multicenter, post-market, observational
Study Phase	Post-market
Study Location	Global
Planned Follow-Up	All subjects will be followed for 24 months
Planned # of Subjects	Up to 2,500 globally
Planned # of Sites	Up to 75
Primary Endpoint	The primary endpoint is the incidence of pneumothorax related to the ENB index procedure rated as Grade 2 or higher according to the Common Terminology Criteria for Adverse Events (CTCAE) scale.
Secondary Endpoints	The following secondary endpoints will be evaluated for all ENB index procedures: 
 1. Incidence of all pneumothorax related to ENB index procedure 2. Incidence of bronchopulmonary hemorrhage related to ENB index procedure rated as Grade 2 or higher according to

	
CTCAE scale
 
 3. Incidence of respiratory failure related to ENB index procedure rated as Grade 4 or higher according to CTCAE scale 4. Subject health status evaluated by EQ-5D questionnaire at all visits 5. Subject satisfaction evaluation at 1-month visit 6. ENB procedure effect on subject productivity and activity using the ENB Productivity and Activity Questionnaire (ENB-PAQ) at 1-month visit 
The following secondary endpoints will be evaluated for all ENB index procedures performed for suspicion of cancer or other lung diseases in a lung lesion:
 
 7. Diagnostic yield 8. Sensitivity 9. Specificity 10. Positive predictive value (PPV) 11. Negative predictive value (NPV) 12. Repeat biopsy rate due to lack of diagnosis during ENB index procedure 13. Adequacy of sample for molecular testing and mutation type (if applicable) 14. Diagnosis 15. Stage at diagnosis (if applicable) 
The following secondary endpoint will be evaluated for all ENB index procedures conducted for placement of fiducial markers:
 
 16. Success rate of accurate placement of fiducial markers demonstrated through follow-up imaging. 
The following secondary endpoint will be evaluated for all ENB index procedures conducted for dye marking in preparation for surgical resection.
 
 17. Success rate of dye marking demonstrated by successful surgical resection 
The following secondary endpoint will be evaluated for all ENB index procedures conducted for a lymph node biopsy:
 
 18. Success rate of obtaining lymph node biopsy to provide stage of diagnosis.
--	--

Randomization	Not applicable
Follow-Up Schedule	Subjects will be evaluated at baseline, procedure, 1 month, 12 months, and 24 months post-index ENB procedure.
Eligibility Criteria	
Inclusion Criteria
 
 1. Subject presents with lung lesion(s) requiring evaluation 2. Subject is willing and able to provide informed consent to participate in the study 3. Subject is candidate for elective ENB procedure 4. Subject is over the age of 18 
Exclusion Criteria
 
 1. The subject is unable or unwilling to comply with study follow-up schedule 2. The subject has participated in an investigational drug or device research study within 30 days of enrollment that would interfere with this study 3. Female subjects who are pregnant or nursing as determined by standard site practices
Statistics	
Endpoint Analyses	Study data will be summarized as descriptive statistics (counts and percentages).
Determination of Sample Size	No formal sample size estimates were conducted. The study is predefined to include up to 2,500 subjects.
Interim Analyses	Interim analyses will be conducted as defined in the publication plan. All interim analyses will be based on complete data for the specified follow-up timepoint.
Pre-Planned Subgroup Analysis	Subgroup analysis of the study endpoints on multiple subsets of study subjects based upon variables such as geography, demographics, investigator experience, and lesion and procedure characteristics are planned.

5.0 Acronyms and Definitions

5.1 Acronyms

eCRF	electronic case report form
CT	computed tomography
CTCAE	Common Terminology Criteria for Adverse Events
EC	ethics committee
ENB	electromagnetic navigation bronchoscopy
EP	existing patient
GCP	good clinical practice
ICF	informed consent form
ICH	International Conference on Harmonisation
ICMJE	International Committee of Medical Journal Editors
IFU	instructions for use
IRB	institutional review board
NCI	National Cancer Institute
NP	new patient
NPBI	New patient, brief interaction (<6 visits and no inpatient hospitalization)
NPCC	New patient, continued care
NPV	negative predictive value
PAQ	Productivity and Activity Questionnaire
PPV	positive predictive value
RDC	remote data capture
SAE	serious adverse event
SAP	statistical analysis plan
TNM	Revised International System for Staging Lung Cancer Classification System
TTNA	transthoracic needle aspiration

CONFIDENTIAL

5.2 Definitions

Bronchopulmonary hemorrhage

A disorder characterized by bleeding from the bronchial wall and/or lung parenchyma. Degree of severity will be classified according to Common Terminology Criteria for Adverse Events (CTCAE) grade as follows:

- Grade 1: Mild symptoms; intervention not indicated
- Grade 2: Moderate symptoms; medical intervention indicated
- Grade 3: Transfusion, radiologic, endoscopic, or operative intervention indicated (e.g., hemostasis of bleeding site)
- Grade 4: Life-threatening respiratory or hemodynamic compromise; intubation or urgent intervention indicated
- Grade 5: Death

Common Terminology Criteria for Adverse Events

A set of criteria for the standardized classification of adverse effects of drugs used in cancer therapy. The CTCAE system is a product of the US National Cancer Institute (NCI)

Diagnostic Test Evaluations

- **Diagnostic Yield:** the proportion of cases that yield a definitive diagnosis. Diagnostic yield will be calculated per patient (as the denominator) and not per the number of lesions biopsied if multiple lesions were biopsied in a single ENB procedure.
- Where a=true positive, b=false positive, c=false negative, and d=true negative:
 - **Sensitivity:** Probability that an ENB-guided biopsy will be positive when malignancy is present (true positive rate): $= a / (a+c)$
 - **Specificity:** Probability that an ENB-guided biopsy will be negative when malignancy is not present (true negative rate): $= d / (b+d)$
 - **Positive predictive value (PPV):** Probability that malignancy is present when an ENB-guided biopsy is positive: $= a / (a+b)$
 - **Negative predictive value (NPV):** Probability that malignancy is not present when an ENB-guided biopsy is negative: $= d / (c+d)$

Existing Patient (EP)

Defined as subjects under care by treating institution more than 30 days prior to the ENB index procedure

Lesion Size

Defined as greatest diameter of target lesion

CONFIDENTIAL

Navigation Accuracy

Distance between tip of the locatable guide and the targeted lung lesion (not done for lymph nodes)

Navigation Success

The proportion of cases in which the operator is able to successfully navigate to the lung target with ENB guidance

Navigation Time

Total time that locatable guide is used in the subject during the ENB procedure

New Patient (NP)

Defined as subjects new to treating institution within 30 days of the ENB procedure and referred by physicians not affiliated with treating institution

NPs will be further categorized as:

- Those with a brief interaction (BI) with treating institution (<6 visits and no inpatient hospitalization): NPBI
- Those who undergo continued care at treating institution: NPCC

Peripheral Lung Lesion

A lesion that is located in the outer third of the lung and difficult to reach by traditional bronchoscopy

Pneumothorax

A disorder characterized by abnormal presence of air in the pleural cavity resulting in the collapse of the lung. Degree of severity will be classified according to CTCAE grade as follows:

- Grade 1: Asymptomatic; clinical or diagnostic observations only; intervention not indicated
- Grade 2: Symptomatic; intervention indicated (e.g., tube placement without sclerosis)
- Grade 3: Sclerosis and/or operative intervention indicated; hospitalization indicated
- Grade 4: Life-threatening consequences; urgent intervention indicated
- Grade 5: Death

Procedure Time

Time between initial introduction of the Locatable Guide into the body and final removal of the Locatable Guide

Repeat biopsy rate due to lack of diagnosis during ENB index procedure

Additional biopsy or biopsies conducted after the ENB-guided index procedure, required due to insufficient tissue collection for diagnosis at the index procedure.

CONFIDENTIAL

Respiratory Failure

A disorder characterized by impaired gas exchange by the respiratory system resulting in hypoxemia and a decrease in oxygenation of the tissues that may be associated with an increase in arterial levels of carbon dioxide. Degree of severity will be classified according to CTCAE grade as follows:

- Grade 4: Life-threatening consequences; urgent intervention, intubation, or ventilatory support indicated
- Grade 5: Death

Stage

Lung cancer staging will be defined according to the Revised International System for Staging Lung Cancer (TNM) Classification System (1, 2). Refer to Appendix 17.2, NAVIGATE_Lung Cancer Staging.

Tissue Adequacy

Tissue adequacy is defined as the proportion of cases in which tissue obtained during the ENB index procedure is adequate for subtyping of lung cancer and molecular testing when appropriate

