8.2.2 Secondary Endpoints

The following secondary endpoints will be evaluated for all ENB index procedures:

1. Incidence of all pneumothorax related to ENB index procedure
2. Incidence of bronchopulmonary hemorrhage related to ENB index procedure rated as Grade 2 or higher according to CTCAE scale
3. Incidence of respiratory failure related to ENB index procedure rated as Grade 4 or higher according to CTCAE scale
4. Subject health status evaluated by EQ-5D questionnaire at all visits
5. Subject satisfaction evaluation at 1-month visit
6. ENB procedure effect on subject productivity and activity using the ENB Productivity and Activity Questionnaire (ENB-PAQ) at 1-month visit

The following secondary endpoints will be evaluated for all ENB index procedures performed for suspicion of cancer or other lung diseases in a lung lesion:

7. Diagnostic yield
8. Sensitivity
9. Specificity

CONFIDENTIAL

10. Positive predictive value (PPV)
11. Negative predictive value (NPV)
12. Repeat biopsy rate due to lack of diagnosis during ENB index procedure
13. Adequacy of sample for molecular testing and mutation type (if applicable)
14. Diagnosis
15. Stage at diagnosis (if applicable)

The following secondary endpoint will be evaluated for all ENB index procedures conducted for placement of fiducial markers:

16. Success rate of accurate placement of fiducial markers demonstrated through follow-up imaging.

The following secondary endpoint will be evaluated for all ENB index procedures conducted for dye marking in preparation for surgical resection.

17. Success rate of dye marking demonstrated by successful surgical resection

The following secondary endpoint will be evaluated for all ENB index procedures conducted for a lymph node biopsy:

18. Success rate of obtaining lymph node biopsy to provide stage of diagnosis.

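### Do sensitivity and NPV need a written rule in Section 5.2 for insufficient-tissue and unverified biopsies?

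*Combined protocol and SAP*

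**What the plan says.** Section 8.2.2 lists endpoints 7 to 15, among them sensitivity (8) and NPV (11), under a heading saying that they "will be evaluated for all ENB index procedures performed for suspicion of cancer or other lung diseases in a lung lesion".

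Section 5.2 defines the accuracy measures with "Where a=true positive, b=false positive, c=false negative, and d=true negative": sensitivity is a/(a+c) and NPV is d/(c+d). The same section defines diagnostic yield as "the proportion of cases that yield a definitive diagnosis" and fixes its unit: "Diagnostic yield will be calculated per patient (as the denominator) and not per the number of lesions biopsied". It also foresees repeat biopsies "required due to insufficient tissue collection for diagnosis at the index procedure".

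On follow-up, the synopsis (Section 4.0) states: "All subjects will be followed for 24 months". Sections 8.6.4.3, 8.6.4.4 and 8.6.5 schedule a lung cancer assessment at 1, 12 and 24 months, with repeat biopsy results where they exist and a review of the medical records. Section 9.5 reports endpoints as counts and percentages. Section 9.6 deals with missing data for the primary endpoint only. Section 9.0 refers to a separate SAP for methods; its text was not part of the material reviewed.

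**The concern.** The four cells require a biopsy that is positive or negative and a lesion that is malignant or not. The protocol recognises index procedures that fit neither description cleanly: those without a definitive diagnosis, and those with too little tissue. If Section 8.2.2 is taken to keep every lesion procedure in the denominator, and Section 5.2 to admit only readable biopsies, the two sections seem to set different denominators.

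A second question is who verifies a negative. No section says that the 12- and 24-month data decide between c and d, or what happens to a negative whose status is never established. Such cases can be imagined. Some new patients are "referred by physicians not affiliated with treating institution", and one category is "Those with a brief interaction (BI) with treating institution". Visits may be by telephone, and subjects can be lost.

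NPV tells a clinician how far to trust a negative biopsy. If two analysts could follow the text and publish clearly different values, that would deserve attention.

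**Working it through.** **1. Do the sections conflict?** Section 8.2.2 sorts endpoints by the purpose of the procedure: lesion, fiducial, dye marking or lymph node. The lesion heading also covers items marked as applying only where relevant (13 and 15), so it does not impose one common denominator. Nor does it say that unreadable samples count as negative. Section 5.2 describes sensitivity as the probability of a positive biopsy given malignancy. A non-diagnostic biopsy in a malignant case is simply not positive, so that wording can keep it in the denominator. The sections can be read together; what is missing is a convention.

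**2. Non-diagnostic results: an upper bound.** Section 6.2.2 gives a weighted mean yield of 73.6%. Weighting Table 1 by its patient column (24 studies, N = 1,521) gives 75.7%. Weights by lesion, which are not listed, might explain the difference. The non-diagnostic share is then at most 26.4% (or 24.3%).

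Let Y be the yield and r the malignancy rate among non-diagnostic cases divided by the rate among diagnosed cases. Assume every definitive result is correct. Counted as negative, sensitivity = Y / (Y + r(1 − Y)); excluded, it is 100% by that assumption.

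- r = 1: 0.736 / 1 = 73.6%
- r = 0.5: 0.736 / 0.868 = 84.8%
- r = 0.25: 0.736 / 0.802 = 91.8%

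The gaps are 26.4, 15.2 and 8.2 points. They overstate the issue, because they remove everything short of a definitive diagnosis. A readable but non-specific negative is still a negative biopsy. Only the truly insufficient samples are in doubt, and the documents give no rate for those.

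**3. A smaller insufficient share.** Assume 65% malignant, sensitivity s = 90% among sufficient samples, no false positives, and an insufficient share i equal in malignant and benign cases. Excluded: sensitivity s, NPV = 0.35 / (0.35 + 0.065) = 84.3%. Counted as negative: sensitivity s(1 − i), NPV = 0.35 / (0.35 + 0.65(1 − s(1 − i))).

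| i | Sensitivity, excluded | Sensitivity, negative | NPV, excluded | NPV, negative |
|---|---|---|---|---|
| 10% | 90.0% | 81.0% | 84.3% | 73.9% |
| 26.4% (upper bound) | 90.0% | 66.2% | 84.3% | 61.5% |

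**4. Unverified negatives.** Let u be the unverified share of negatives. Moving all of them from true negative to false negative changes NPV by exactly u, whatever the prevalence. At assumed shares of 5%, 10% and 20% the gap is 5, 10 and 20 points.

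For sensitivity, assume 60% malignant and 75% sensitivity, so TP = 0.45, FN = 0.15, TN = 0.40 and negatives = 0.55. With equal unverified shares among false and true negatives:

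- u = 5%: 0.45/0.5925 − 0.45/0.62 = 3.4 points
- u = 10%: 0.45/0.585 − 0.45/0.64 = 6.6 points
- u = 20%: 0.45/0.57 − 0.45/0.68 = 12.8 points

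Over every split from all benign to all malignant, the ranges are 3.3 to 3.6, 6.3 to 7.6 and 11.6 to 16.8 points.

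**5. Is a large unverified share likely?** The documents do not say. The brief-interaction category means fewer than six visits, and the whole study schedule is five (baseline, procedure, 1, 12 and 24 months), so it is compatible with complete follow-up. Telephone visits come with a record review. Section 8.4.2 excludes subjects who cannot or will not follow the schedule. Section 8.5 requires calls and a certified letter before a subject counts as lost.

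**6. What will the report show anyway?** Yield is a per-patient count and percentage for the same procedures, so its complement is the non-diagnostic number. Repeat biopsy rate and diagnosis are separate endpoints, and Section 9.1 adds cross tabulations and subject listings. Only the count of unverified negatives has no named place.

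**The case for a change.** The best case for a change is that the silence is real and the remedy cheap. No section names a reference standard for malignancy. The one specific use given for 24-month follow-up, in Section 6.1, is relating stage to survival. The Medical Monitor in Section 12.1 adjudicates adverse events, not diagnoses. The reason in Section 9.6 for not imputing is that the primary endpoint is peri-procedural, which does not carry over to endpoints that need follow-up. The interim analyses in Section 9.8 are triggered at 1 month, before most verification is possible. A sentence in Section 5.2 would remove the doubt.

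Much of this stands as description. The cells are not tied to the follow-up data, the per-patient unit is stated only for yield, and any accuracy figures reported at an interim analysis would be provisional. It does not show that a stated rule gives a wrong result. Counting insufficient tissue as negative is one convention among several, so a one-line rule would settle a debatable choice rather than correct an error. A quick rule can also do harm. If any malignant pathology, including the index sample itself, proved malignancy, then b = 0, and specificity d/(0 + d) and PPV a/(a + 0) would be 100% by construction.

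**Conclusion.** No change to the plan follows. Section 5.2 leaves a definition unwritten; it does not contradict Section 8.2.2. The measures concerned are secondary and descriptive, in a single-arm study with no formal sample size (Section 9.3), and the primary pneumothorax endpoint does not depend on them. The data needed to classify a negative biopsy are already required to 24 months, and an analyst can state the convention used and show the alternatives. The separate SAP is the proper home for that detail and may already hold it.

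The possible effect is not trivial. In the illustrations it is 9.0 points of sensitivity at an assumed 10% insufficient share, and NPV moves point for point with the unverified share of negatives. These figures rest on assumed prevalence, sensitivity, insufficient share and unverified share, none of which the documents give. The 26.4-point gap is an upper bound that treats every case without a definitive diagnosis as unreadable. The figures are a reason to read the accuracy results together with the reported yield.

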6.0 Introduction**6.1 Background/Justification of Investigation**

Rapid and precise diagnosis of suspicious lesions is crucial to determine the optimal treatment for lung disease. Diagnosis of peripheral lung lesions, which comprise 25-30% of all lung lesions, is particularly challenging (3, 4).

Technologies that allow for earlier diagnosis and treatment of malignant lung disease are crucial for improving survival rates. According to the American Cancer Society's 2014 estimates, the survival rate for distant (metastasized) lung cancer is 4%, compared to 26% for regional cancer and 54% for localized cancer (5).

Electromagnetic navigation bronchoscopy (ENB)TM is an image-guided approach that uses 3D-reconstructed computed tomography (CT)-scan and sensor location technology to guide a steerable endoscopic probe to peripheral lung lesions that may be beyond the reach of conventional bronchoscopes (5-7).

Over 24 original research articles have been published describing outcomes following ENB to aid in the diagnosis of peripheral lung lesions and mediastinal lymph nodes (3, 6-28). Diagnostic yield aided by ENB in these studies has ranged from 59.0% to 94.0%, with rates generally higher in more recent analyses (3, 6, 9, 10, 15, 17, 18, 20, 23-25).

ENB is also associated with a more favorable safety profile than alternative techniques; in a meta-analysis of 15 studies representing data from over 1000 lung nodules, the pneumothorax

rate after ENB was only 3.1% (29). In comparison, in a meta-analysis of 19 studies, the median pneumothorax incidence rate following CT-guided transthoracic biopsy was 25% (range 4% to 60%) (30).

Despite these promising results, outcomes following ENB are widely varied and most evidence to date is based on single-center analyses (21 of the 24 published studies) with only 3 studies enrolling greater than 100 subjects (see Table 1). The impact of user/center experience, patient risk factors, and lesion characteristics remains largely unexplored in a large multi-center study. In addition, further information is needed about the use of ENB to place dye markers to allow biopsy and surgery in the same procedure, the use of ENB to place fiducials to enable radiation therapy, the adequacy of cells and tissue captured using ENB for genomic testing, the impact of ENB on stage of diagnosis, and the cost effectiveness of ENB.

The proposed post-market study will enroll up to 2,500 consecutive subjects at up to 75 sites worldwide, making it the largest prospective ENB clinical study to date. The 24-month follow-up of this study will also allow an assessment of the correlation between stage of diagnosis and long-term survival rates, in contrast to most prior ENB studies that evaluated only diagnostic yield and acute complication rates.

The objective of this prospective, single-arm, multicenter, post-market, observational, study is to evaluate outcomes following electromagnetic navigation bronchoscopy (ENB) procedures using the superDimension™ navigation system.

